The second 4-month follow-up visit (4FV2) will occur 3-5 days after the 4FV1 visit in the morning for participants in the muscle biopsy substudy who had a viable muscle biopsy sample at BV2 only. After an 8-hour overnight fast, participants will undergo a muscle biopsy of the *vastus lateralis* followed by a snack. Participants will receive a phone call 2-4 days following the procedure to check that they are not experiencing any adverse effects that may be related to the procedure. The study physician ([name]) will be notified of any adverse effects related to the muscle biopsy procedure and any necessary action taken.

The 12-month follow-up visit (12FV) will occur during week 52 of the intervention. After an 8-hour overnight fast, participants will have their vitals taken and blood drawn for analyses of serum 25(OH)D and 1,25(OH)D, plasma PTH, metabolic panel, and storage followed by a snack. Lower extremity muscle power and strength, physical performance, grip strength, postural sway, stair climb, and gait velocity will be measured. The CHAMPS Physical Activity Questionnaire, MAT-sf, arthritis and joint pain questionnaire, DSST, CES-D, the MoCA, and sun exposure questionnaire will be administered. Medical history and current medications and dietary supplements will be reviewed. Monthly fall calendars will be collected and reviewed. Participants will return the study supplement bottles with any remaining pills. Participants will then be told of their randomization assignment.

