Participants will be randomized to either 2000 IU/d of vitamin D₃ or placebo for 12 months. The vitamin D₃ supplements and matching placebo pills will be manufactured by Tishcon Corp (Salisbury, MD). The proposed dose is expected to increase 25(OH)D concentrations by \sim 14 ng/mL.^{20,21} Previous vitamin D supplement dosing studies have observed a plateau in the increase in 25(OH)D concentrations in 6 to 8 weeks.^{20,22,23} In a recent dose-response study, a vitamin D₃ dose of 1600 IU/d increased 25(OH)D concentrations from $<$ 20 ng/mL to \geq 30 ng/mL over 1 year in 97.5% of participants.²⁴ However, we will measure serum 25(OH)D at the 4-month visit and increase the vitamin D₃ dose to 4,000 IU/d in participants in the intervention group with 25(OH)D concentrations $<$ 30 ng/mL (for every participant in the intervention group that has to increase their vitamin D₃ supplement dose to 2 pills/d after the 4-month follow-up visit, a random participant from the placebo group will also be instructed to take 2 placebo pills/d). Supplements will be dispensed at baseline and at the 4-month visit. Participants will be instructed to maintain their regular dietary intake and typical physical activity level and instructed to refrain from starting any other dietary supplements or changing the frequency/dose of any supplements they are currently using during the study. A brown bag review will be done at each visit of all

dietary supplements participants are currently taking; and the brand and type, frequency, and dose of vitamin D and calcium will be recorded on the medication inventory. Supplement adherence will be monitored monthly via phone calls and the remaining supplement pills counted at the 4- and 12-month visits. Since the half-life of 25(OH)D is ~2-3 weeks,²⁷ occasional missed pills should have a minimal effect on 25(OH)D concentrations. The neuromuscular function assessments, mechanistic studies of the muscle biopsy sample, and assessments of 25(OH)D and 1,25(OH)₂D will be conducted by study staff and investigators blinded to the vitamin D intervention assignment.

Outcome measures

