Vitamin D status: Fasting blood samples will be collected in the morning by trained and certified phlebotomists at baseline and 4-month and 12-month follow-up. Blood samples will be sent to LabCorp for assessment of serum 25(OH)D for screening purposes and at 4-month follow-up to assess 25(OH)D response to vitamin D supplementation and for assessment of serum calcium at each visit. After processing, approximately 4 ml of the blood from each visit will be aliquotted and stored at -80°C until it is shipped to the Clinical and Analytical Lab (CACL) at the Human Nutrition Research Center on Aging at Tufts University where the samples will be stored at -80°C until analysis. Serum total (D₂ and D₃) 25(OH)D will be assessed in duplicate using LC/MS/MS (Waters Acquity UPLC with TQD triple quadrupole mass spectrometer; CV: 6%) along with the 25(OH)D standard reference material (SRM 972) developed by the National Institute of Standards and Technology and the National Institutes of Health Office of Dietary Supplements for assay calibration.⁴⁵ Serum 1,25(OH)₂D will also be assessed in duplicate using the 5500 QTRAP LC/MS/MS System (AB Sciex LLC) with Electrospray after immunoaffinity extraction, 4-phenyl-1,2,4-triazole-3,5-dione (PTAD)

derivatization, and methylamine adduction (intra- and interassay CVs of 5% and 8.5%, respectively). Repeat analyses will be conducted when duplicate samples differ by 10% or more. **Storage:** Approximately 10 ml of blood (serum and plasma) from each visit will be stored at -80°C in the Pepper Tissue Repository (IRB# 1219) for storage. Any person wishing to use this blood will obtain IRB approval first.

Season: The season in which the participant is screened for eligibility will be obtained to examine if the season of enrollment affects the outcomes due to seasonal effects on endogenous vitamin D synthesis and 25(OH)D concentrations.

Supplement adherence: Although we will attempt to enhance adherence by monthly calls to participants, there may be inter-individual variability in adherence to supplementation. At the 4 and 12-month study visits, participants will be asked to return any unused supplements for a pill count to determine participant adherence. Our primary analyses will be an intent-to-treat analysis of the effects of the vitamin D intervention, but secondary analyses will include adherence as a covariate.

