Calcium and vitamin D intake: Calcium and vitamin D intake from diet and supplements will be assessed at baseline using a short calcium and vitamin D intake questionnaire.

Cognitive function will be assessed during screening using the Montreal Cognitive Assessment (MoCA), participants must score ≥ 18 to be eligible. We will also assess psychomotor speed, attention, and working memory using the Digit Symbol Substitution Test (DSST). Participants are given a series of numbered symbols and then asked to draw the appropriate symbols below a list of random numbers. The score is the number of correctly made matches in 2 minutes (120 seconds). The cognitive function tests will be audio recorded by the assessor using a hand held digital recorder. The recordings will be used to properly score the tests as well as be available for quality control testing. The recordings will be deleted once the study is over and the data that was entered has been verified.

Mood will be assessed using the 20-item Center for Epidemiologic Studies Depression Scale (CES-D).

Demographic characteristics including age, gender, race, education level, and socio-economic status will be recorded and used as covariates if necessary.

Body mass index (BMI) will be calculated from measured height and weight.

Physical activity will be measured using the CHAMPS Physical Activity Questionnaire for Older Adults¹⁷ at baseline, 4- and 12-month follow-up. In addition to being a strong correlate of the neuromuscular function measures, more physically active participants will likely have increased sun exposure, and therefore, may have higher endogenous vitamin D production.

Activities of daily living will be assessed using the Mobility Assessment Tool – Short Form (MAT-sf) at baseline, 4- and 12-month follow-up. This is a novel, computerized tool for self-assessment of functional performance designed to reduce bias from factors such as age, gender and body image.

Sun exposure will be assessed at baseline, 4- and 12-month follow-up using a modified version of the NHANES Dermatology Questionnaire that includes questions on sun exposure and sun protection habits.

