We will examine the distributions of all continuous outcomes of interest, and will transform them to approximate normality if the outcomes show a strong departure from normality as evidenced by examining Q-Q plots and performing the Shapiro-Wilk test. Outliers will be examined on the chosen scale (original or transformed) and may be set to missing if they are 3 or more interquartile ranges above the 75th percentile or below the 25th percentile. Plausible biologic values may be retained even if they are outliers. Implausible biologic values may be set to missing based on a review of health-related events (e.g., AEs related to pain, fractures, surgery) in the interval surrounding the collection of the measurements.

The primary outcome for this trial will be the 12-month measure of muscle power. For the muscle biopsy substudy, the primary outcome will be the change in type II muscle fibers over 4-months. Our primary statistical analyses will proceed on the “intent-to-treat” principle in which data from all randomized participants are used to test the primary hypotheses that compared to placebo, vitamin D₃ supplementation will result in increases in lower extremity muscle power and strength, and improvements in physical performance (expanded SPPB, TUG, and 20-m walk speed) and balance. Even if participants wish to discontinue the supplements, we will still attempt to follow them for outcomes in order to carry out intent-to-treat analysis at 12 months. Characteristics of the participants missing the 12-month follow-up outcomes will be compared to participants without missing data using chi-square tests and t-tests to determine if there are any differences with regard to intervention group, demographic characteristics, and baseline neuromuscular function outcomes. If a particular group exhibits markedly higher drop-out rates, we will attempt to identify baseline covariates that predict attrition. If such covariates can be identified, the analyses of outcome measures may need to be stratified according to these comparisons to decrease bias. We will use a mixed model with an unstructured covariance matrix to model after-treatment neuromuscular function outcomes between the two groups by time, with adjustment for

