the baseline neuromuscular function measure, age, gender, and race, using data from baseline, 4, and 12 months, and estimating the baseline to 12 month change using linear contrasts. In secondary analyses, we will fit linear contrasts to compare whether the change between the two groups at 4 months differs from the change at 12 months. These analyses will be adjusted for age, gender, race, and season, as we anticipate there will be an effect of season on the change from baseline and 12 months. If the analyses of the characteristics of those missing the 12-month outcome data indicate that the missing data are informative, we will also consider using the 4-month outcome data to impute the 12-month outcome, using the trajectory models to predict the 12-month outcome.

We will examine factors that may influence the measured responses to the intervention. We anticipate that not all individuals will respond to the vitamin D₃ dose in a similar manner due to genetic differences⁵⁰⁻⁵² as well as differences in BMI,^{53,54} health status, and adherence.³ First, individuals in the vitamin D intervention group who have low adherence (<80%) will be excluded from the analysis. We will also investigate treatment effects by attained 25(OH)D concentrations including only those in the intervention group whose 12-month 25(OH)D concentrations are ≥30 ng/mL. We will also fit models that include BMI, health status, and other variables to determine if they account for any of the variation in response to the intervention on changes in the outcomes. For our exploratory outcome of falls, we will use a generalized estimating equation (GEE) approach to model repeated measures, assuming a Poisson distribution, to compare the rate of falls in each group with adjustment for age, gender, and race.⁵⁵ Differences in, or reasons for, attrition rates between study groups may complicate the analysis of the primary outcomes. Therefore, the attrition rates will also be compared and, if a particular group exhibits markedly higher drop-out rates, we will attempt to identify baseline covariates that predict attrition. If such covariates can be identified, the analyses of outcome measures may need to be stratified according to these comparisons to decrease bias.

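### Two supportive analyses filter the vitamin D arm only (adherence below 80%; 12-month 25(OH)D of 30 ng/mL or more), so their comparison with placebo is not randomised

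*Combined protocol and SAP*

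**What the plan says.** The Statistical Analyses section makes intent-to-treat the primary analysis, "in which data from all randomized participants are used to test the primary hypotheses". The model adjusts for the baseline measure, age, gender and race; season is added in secondary analyses.

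The same section then turns to factors that may influence response and sets two selection rules:

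- Adherence: "individuals in the vitamin D intervention group who have low adherence (<80%) will be excluded from the analysis".
- Attained level: treatment effects are examined "including only those in the intervention group whose 12-month 25(OH)D concentrations are ≥30 ng/mL".

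Both rules name the vitamin D arm only, and the document gives no placebo counterpart for either.

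Adherence data are not limited to one arm. Under Covariates, Supplement adherence, "participants will be asked to return any unused supplements for a pill count to determine participant adherence" at 4 and 12 months, and the 12-month visit description says "Participants will return the study supplement bottles with any remaining pills". The Supplement adherence paragraph also plans secondary analyses with adherence as a covariate. The document does not say how that relates to the exclusion rule.

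**The concern.** Adherence and attained 25(OH)D are both observed after randomisation. Selecting on them in one arm leaves a subset of the vitamin D group facing the whole placebo group, so randomisation no longer supports the comparison. If people who take their pills, or who reach 30 ng/mL, would have had better 12-month power anyway, given their baseline power, age, gender and race, that advantage is counted as a vitamin D effect.

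For attained 25(OH)D the document itself gives a plausible route. Under Covariates, Physical activity, it says: "In addition to being a strong correlate of the neuromuscular function measures, more physically active participants will likely have increased sun exposure", and so possibly higher endogenous vitamin D. Activity is not in the main model's adjustment set. Baseline power will absorb part of this, but not necessarily all.

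What is at stake is interpretation. The trial asks whether raising 25(OH)D to 30 ng/mL or more helps, so a favourable result among adherers or attainers could easily be quoted as the answer even if the intent-to-treat result is null.

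**Working it through.** **Inputs from Statistical Power:** SD 0.444 W/kg, baseline-to-12-month correlation 0.708, design difference 0.174 W/kg, 125 participants allocated 1:1, two-sided 0.05.

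**Assumed, because the documents give neither:** the share p of the active arm removed (10% to 30%), and the correlation ρ between the selection variable and baseline-adjusted power (0 to 0.3).

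**1. The plan's own figure.** Residual SD = 0.444 × √(1 − 0.708²) = 0.3136 W/kg. With 62.5 per arm, SE = 0.3136 × √(2/62.5) = 0.0561, and 0.174/0.0561 = 3.10. Power is Φ(3.10 − 1.96), about 87%, which agrees with the stated figure of more than 80%. The present point does not affect it.

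**2. Bias from filtering one arm, with no true effect.** If the lowest fraction p on a normally distributed selection variable is dropped from the active arm only:

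bias = ρ × 0.3136 × φ(z_p)/(1 − p)

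At ρ = 0.3, the multiplier 0.3 × 0.3136 is 0.0941. The rejection rates come from 20,000 simulated trials with 62 per arm, testing baseline-adjusted residuals at the two-sided 0.05 level.

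| Share dropped, active arm only | φ(z_p)/(1 − p) | Bias, W/kg | Share of 0.174 | Type I error |
|---|---|---|---|---|
| 2.5% | 0.060 | 0.006 | 3% | 5.1% |
| 10% | 0.195 | 0.018 | 11% | 6.1% |
| 20% | 0.350 | 0.033 | 19% | 8.3% |
| 30% | 0.497 | 0.047 | 27% | 11.4% |

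A normal approximation gives 6.2%, 8.7% and 11.9% for the last three rows. At ρ = 0.15, the 10%, 20% and 30% rows fall to 5.4%, 5.7% and 6.6%. At ρ = 0 the bias is zero and rejection is 4.9% to 5.2%.

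**3. The attained-level rule.** The Vitamin D intervention section cites a dose-response study in which 30 ng/mL was reached "over 1 year in 97.5% of participants". If that held here, 2.5% would be dropped and the first row applies: at most 0.006 W/kg and a type I error of about 5%.

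**4. The same adherence rule in both arms.** At ρ = 0.3 with 10% to 30% dropped from each arm, bias is within 0.001 W/kg and rejection is 4.8% to 5.1%. This assumes that adherence behaves alike in both arms. If 10% of active but 20% of placebo participants are dropped, bias is about 0.018 − 0.033 = −0.015 W/kg and rejection is 5.8%.

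**The case against.** The strongest reply has four parts.

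- **These are supportive analyses.** Intent-to-treat is primary, adherence analyses are called secondary under Supplement adherence, and both rules sit in a paragraph about influences on response. This is right and it limits the point. However, that paragraph does not itself label the two analyses secondary or non-randomised.
- **The documented route and the larger bias belong to different rules.** The activity route concerns attained 25(OH)D, where few exclusions may occur. A mean rise of about 14 ng/mL from the eligibility floor of 18 gives 32, and vitamin D participants below 30 at month 4 have their dose increased. The larger figures need a healthy-adherer effect, for which the documents offer no evidence. This stands as a limit on size. Still, the 97.5% figure comes from another dose (1600 IU/d) and starting range (below 20 ng/mL), and the plan itself anticipates non-adherence and participants below 30 at month 4.
- **A two-arm exclusion is still selection after randomisation.** True. In the unequal case above it does about as badly as the one-arm rule at 10%, with the sign reversed (−0.015 against +0.018 W/kg). It removes the built-in asymmetry but does not restore randomisation.
- **The attained-level sentence may mean a description within the vitamin D arm.** Possible, but it speaks of treatment effects and names no comparator.

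The plan also intends separate models with BMI, health status and other variables. These could reduce confounding, but they are not tied to the two filtered comparisons.

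**Conclusion.** The concern holds as a matter of design. Followed as written, both rules compare a selected active arm with an unselected placebo arm. For adherence this is avoidable, because pill counts are taken in both arms.

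The size is unknown. Under the assumptions above (ρ from 0 to 0.3; 10% to 30% dropped), bias runs from 0 to 0.047 W/kg and type I error from about 5% to between 11% and 12%. The upper end needs both the highest correlation and the largest exclusion. For the attained-level rule the bias is likely to be small if attainment is close to the cited 97.5%. The primary analysis and its power are untouched. The change should be made because the asymmetry is plain in the text and cheap to remove, not because a large bias has been shown.

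**What to change.** In Statistical Analyses:

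1. Apply the below-80% adherence exclusion to both arms. Compute adherence from the planned pill counts against each participant's own assigned number of pills, since some in both arms are assigned two a day after month 4. Report the share excluded by arm, and state that the comparison assumes adherence behaves alike in the two blinded arms.
2. Label the attained-25(OH)D subset descriptive and non-randomised, and name its comparator, if any. It cannot be mirrored in placebo, because treatment itself changes 25(OH)D.
3. State that neither analysis can override the intent-to-treat result, and say whether the adherence-as-covariate analysis is planned alongside the exclusion. That analysis need not change on this ground.

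The cost is two or three sentences and no new data. The change is most credible if made before unblinded analysis.

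Optionally, add a randomisation-based instrumental-variable estimate. A version per ng/mL must state that assignment acts only through 25(OH)D and must give the assumed dose-response form; a linear form would not test the 30 ng/mL threshold. A complier-average version adds one model and a wider interval. With an assumed 80% compliers, its SE is 0.0563/0.8 = 0.0704 W/kg, a factor of 1.25, where 0.0563 = 0.3136 × √(2/62). The first three changes do not depend on this option.

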Growing evidence indicates that vitamin D's effect on reducing falls is mediated by improvements in neuromuscular function.⁶⁻⁸ We and others have shown associations between 25(OH)D concentrations and muscle strength and physical performance measures associated with fall risk (e.g., gait, balance) in observational studies.^{6,9-13} Yet trials of vitamin D supplementation on changes in muscle strength and physical performance are equivocal,¹⁴ likely due to inadequate trial duration, small sample sizes, insufficient vitamin D dose, and sample heterogeneity. Moreover, vitamin D's effects on the mechanisms underlying neuromuscular function are not well understood. Determining whether increasing 25(OH)D concentrations to ≥ 30 ng/mL will improve neuromuscular deficits that are risk factors for falls and elucidating the underlying physiological mechanisms linking vitamin D and neuromuscular function could change clinical practice by providing evidence to guide vitamin D supplementation recommendations for neuromuscular-related outcomes in older adults.

Objectives

To conduct a 12-month, double-blind randomized placebo controlled trial in 136 older (65-89 yrs) men and women with initial 25(OH)D concentrations of 18- <30 ng/mL to determine the effect of increasing 25(OH)D concentrations to ≥ 30 ng/mL through vitamin D₃ supplementation on 1) change in neuromuscular functions that are established risk-factors for falls in older adults; and 2) changes in the underlying physiological mechanisms over 4 months in a subset of 36 randomly selected participants. Participants will be randomized to 2000 IU/d of vitamin D₃ (a dose expected to increase 25(OH)D concentrations by ~ 14 ng/mL) or placebo.

Hypothesis 1: Compared to participants randomized to placebo, participants randomized to vitamin D₃ will have increased lower extremity muscle power and strength, increased physical performance, decreased postural sway, and reduced rate of falls over 12 months.

Hypothesis 2: Compared to participants randomized to placebo, participants randomized to vitamin D₃ will have increased type II muscle fibers, muscle fiber force, and myofiber regeneration, and decreased muscle fiber denervation over 4 months.

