Lower extremity muscle strength and power, physical performance, and postural sway will be assessed at baseline, 4 months and 12 months and falls assessed monthly. Muscle biopsies of the *vastus lateralis* will be taken at baseline and 4 months to assess muscle fiber type, contractility, and denervation, and number and differentiation stage of satellite cells. The primary outcomes are change in lower extremity muscle power (Hypothesis 1) and change in percentage of type II (fast-twitch) muscle fibers (Hypothesis 2). Secondary outcomes include change in lower extremity muscle strength, physical performance, and postural sway (Hypothesis 1) and muscle fiber contractility, muscle fiber denervation, and number and differentiation of satellite cells (Hypothesis 2). Falls will also be assessed as an exploratory outcome (Hypothesis 1).

Methods and Measures

Experimental Overview/Study Design

This study is a 12-month, double-blind randomized placebo controlled trial in 136 older (65-89 yrs) men and women with initial 25(OH)D concentrations of 18-<30 ng/mL to determine the effect of increasing 25(OH)D concentrations to ≥ 30 ng/mL through vitamin D₃ supplementation on 1) change in neuromuscular functions that are established risk-factors for falls in older adults and 2) changes in the underlying physiological mechanisms over 4 months in a subset of 36 randomly selected participants. Participants will be randomized to vitamin D₃ (2000 IU/d) or matching placebo in a 1:1 ratio stratified by gender and race.

Recruitment of study participants

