Gait velocity will be measured using a 4.88 m long instrumented carpet (GAITRite, CIR Systems Inc., Clifton, NJ). The carpet is composed of 18,432 force sensing sensors arranged in a 48 wide x 384 long grid. Data are sampled at either 60, 120, or 240 Hz. The GAITRite is interfaced with a laptop computer that runs software to calculate variables related to gait performance. The GAITRite system is a valid instrument for determining gait velocity and other spatiotemporal parameters. In the testing procedures, participants walk across the carpet, beginning 2 m in front of the carpet and walking 2 m past the end of the carpet to allow for acceleration and deceleration. Participants make multiple passes over the carpet at either the preferred (4 trials) or fast (4 trials) velocity. At the preferred velocity, participants are told to walk “at a pace that feels comfortable to you (as if you were walking to the mailbox or window shopping at the mall).” At the fast velocity the instructions are to walk “as quickly as you can without running.” The software calculates individual trial and average data on gait velocity and spatiotemporal gait characteristics and these data can be exported for further analysis. Summary data on velocity (m/sec; averaged over the 4 usual and 4 fast trials) and the average of the left and right leg for double support (percent of cycle), single support (percent of cycle), stance (percent of cycle), swing (percent of cycle), stride length (cm), and base width (cm) for both the usual and fast trials will be used in analysis.

Falls will be defined as an event whereby an individual unexpectedly comes to rest on the ground or another lower level. Participants will be provided monthly fall calendars, considered the “gold standard”,³⁸ and asked to mark any falls that occur on the calendar. Completion of monthly fall calendars will be monitored via monthly phone calls and collected at the 4- and 12-month visits. Total number of falls over the 12-month follow-up will be used in analysis.

Single fiber-type composition and fiber size will be examined in muscle biopsies using the ATPase, pH 9.4 and 4.6 technique, combined with laminin immunostaining in 10 μ m muscle sections and the absolute and relative number of type I, IIA, IIX fiber subtypes and their cross-sectional area quantified. The relative number of fiber type and their cross-sectional area at baseline and 4-month follow-up will be used in analysis.

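### The exploratory falls model omits baseline neuromuscular function, giving up a small and almost free gain in precision

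*Combined protocol and SAP*

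**What the plan says.** - **Falls model.** Statistical Analyses specifies a Poisson GEE for the repeated fall counts, its purpose being "to compare the rate of falls in each group with adjustment for age, gender, and race". The falls paragraph under Outcome measures adds: "Total number of falls over the 12-month follow-up will be used in analysis". The Objectives class falls as exploratory, although a reduced fall rate is part of Hypothesis 1.
- **Function as a fall risk factor.** The Objectives define the first aim as "change in neuromuscular functions that are established risk-factors for falls in older adults".
- **Timing.** "Lower extremity muscle strength and power, physical performance, and postural sway will be assessed at baseline, 4 months and 12 months and falls assessed monthly". Table 2 and the description of BV1 place the expanded SPPB, leg power, strength, sway and gait at BV1. Treatment is assigned at the end of baseline visit 2.
- **Comparison model.** The mixed model for the neuromuscular outcomes adjusts for "the baseline neuromuscular function measure, age, gender, and race".
- **Other covariates.** Statistical Analyses also plans models with BMI, health status and unnamed further variables, to explain variation in response. Nothing there puts baseline function into the falls comparison.

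**The concern.** In the main trial, each neuromuscular outcome is adjusted for its own baseline value. Falls have no baseline count, so that route is closed, and the falls model carries no measure of function at entry. Two of its three covariates, gender and race, are already balanced by stratified randomisation. Function is not a stratification factor, and the protocol itself ties it to falls.

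Two things are at stake, both modest. Between-person variation in fall rate that baseline function could explain stays in the standard error. And if the arms happen to differ in baseline function, readers will ask for an adjusted result; a covariate chosen at that stage would be chosen after seeing the data.

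**Working it through.** **1. The plan's own figures.** There is no rate, effect size or power for falls to reproduce. Statistical Power covers leg power only: difference 0.174 W/kg, SD 0.444, correlation 0.708, 125 analysed. Residual SD = 0.444 × √(1 − 0.708²) = 0.314, and power is 0.873, so the claim of more than 80% holds. From this I take 125 analysed, or 62.5 per arm.

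**2. Assumed inputs for falls (none from the documents).** Control rate μ₀ = 0.5, 1.0 or 1.5 per person-year; one year of follow-up; overdispersion k = 0.5 to 2; true rate ratio 0.70, so μ₁ = 0.7μ₀; fall-rate ratio g = 1.2 to 1.5 per SD of baseline function.

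**3. Without the covariate.** Var(log RR) = [(1/μ₀ + k) + (1/μ₁ + k)] / 62.5. Power for a rate ratio of 0.70 is 16% (μ₀ = 0.5, k = 2) to 41% (μ₀ = 1.5, k = 0.5). With no overdispersion and 1.5 falls per year it reaches 60%.

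**4. With the covariate, efficient weighting.** The covariate contributes v = exp[(ln g)²] − 1, and k falls to k′ = (1 + k)/(1 + v) − 1. Example with μ₀ = 1.0, k = 1, g = 1.5:
- v = 0.179 and k′ = 2/1.179 − 1 = 0.697.
- Bracket before: 1 + 1.429 + 2 × 1 = 4.429. After: 1 + 1.429 + 2 × 0.697 = 3.822.
- SE ratio = √(3.822/4.429) = 0.929; power moves from 0.268 to 0.302.

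Over the whole grid the SE falls by about 1% (ratio 0.992 at μ₀ = 0.5, k = 0.5, g = 1.2) to 9% (ratio 0.909 at μ₀ = 1.5, k = 0.5, g = 1.5). For rates up to 1.0 the largest fall is 7% (ratio 0.927). Power rises by 0.2 to 7 points.

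**5. With the covariate, Poisson weighting.** Step 4 assumes negative-binomial-type weights. A Poisson model gives more weight to people with high expected counts, so the dispersion term becomes k′(1 + v) = k − v, which is larger than k′. In the same example the bracket is 2.429 + 2 × (1 − 0.179) = 4.071, and the SE ratio is √(4.071/4.429) = 0.959. The gain is 4%, not 7%.

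**6. Simulation.** Poisson regression with robust SE, 124 participants, 1,500 runs per scenario, one total per person; age, gender and race not modelled. Rates 0.5 and 1.0, k = 0.5 to 2, rate ratio 0.70:

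| g per SD | Empirical SE ratio, adjusted / unadjusted | Change in power |
|---|---|---|
| 1.0 | 1.002 to 1.007 | about −0.4 to +0.7 points |
| 1.2 | 0.985 to 1.001 | about 0 to +1 point |
| 1.5 | 0.950 to 0.984 | about +1 to +3 points |

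The step 5 example gives 0.964 in simulation, against 0.959 by formula. A rate of 1.5 was not simulated.

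**The case against.** The strongest reply is that this is preference, not error. Falls are exploratory, the model is prespecified, and leaving out a prognostic covariate does not bias a randomised comparison. With no baseline fall count there is no own-baseline term to restore. All of that stands.

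The gain may also be smaller than shown. Baseline function overlaps with age, gender and race, which are already in the model but were left out of the simulation. Table 1 limits entry to low SPPB scores and requires self-reported difficulty, which narrows the spread of function. Both points push towards the lower end of the range.

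The choice of covariate is a judgement too. The document's most specific link between one measure and fall risk is for sway, under Outcome measures, not the expanded SPPB. Leg power is a weaker candidate because the power rig has testing exclusions, so it may be missing for some participants.

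The planned models with further variables do not answer the point: they concern variation in response and name no function measure for falls.

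A reader might infer three stronger things that the documents do not support:
- **That chance imbalance in function biases the rate ratio.** Imbalance in a single trial is real, but across randomisations it is the same variation that the robust standard error already covers.
- **That the documents show falls to be underpowered.** They give no falls inputs; the power figures here are assumption-based.
- **That adjustment would rescue the falls comparison.** In every scenario tried with the covariate, power for a rate ratio of 0.70 stays below 50%.

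**Conclusion.** The point holds as a minor, optional improvement. The falls model leaves out a class of baseline measures that the protocol itself links to falls and already collects before treatment assignment. The planned analysis remains valid.

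The expected benefit is a fall of about 0 to 5% in the standard error of the log rate ratio for a Poisson/robust-SE model at 0.5 to 1.0 falls per person-year, probably towards the lower end. The efficient-weighting bound is about 9%, reached only at 1.5 falls per year with a strong covariate. If baseline function does not predict falls, the cost is about 0.2 to 0.7% of the standard error. The fall rate, the dispersion, the true rate ratio and the strength of the covariate are all assumed. No conclusion of the trial is likely to turn on it; fixing the covariate in advance is worth about as much as the precision.

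**What to change.** In Statistical Analyses, add one named continuous baseline function covariate to the falls GEE alongside age, gender and race. The BV1 expanded SPPB score is a practical choice: it is a performance summary scheduled for all participants, without the testing exclusions stated for the power rig and the dynamometer. A single named sway parameter would also be defensible. What matters is that one is fixed before unblinding. If the team prefers to keep the current model as the main falls analysis, the adjusted model can be a prespecified sensitivity analysis.

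The cost is one line in the analysis plan. No new data are needed, and the sample size and the primary analysis are unaffected.
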